An intervention to Promote Positive Peer Relationships and Reduce Prejudice and Bias in Childhood, July 16, 2025

Study Protocol

The objectives of this project was to test the beneficial impacts of an intervention, *Developing Inclusive Youth (DIY)*, for outcome measures reflecting increasing school belonging, classroom support, and intergroup attitudes (reducing stereotypes and biases) relative to a counterfactual (the business-as-usual control condition). A multi-site within-school randomized control trial (RCT) intervention design was employed to promote positive intergroup relationships and to reduce prejudice in childhood. The program was implemented under routine conditions in authentic education settings (grades 3, 4, and 5) which in this case was a large ethnically diverse public school district in the Maryland suburbs of Washington, D.C. The program had two components to it: 1) individualized viewing of a web-based curriculum tool depicting peer inclusion and exclusion scenarios; and 2) a group experience in which the teacher led a classroom discussion session that immediately followed students' use of the tool.

The web-based curriculum tool developed by the P.I.'s research team was an opportunity to view depictions of peer groups discussing everyday situations involving inclusion and exclusion, with a focus on multiple target groups: race and ethnicity (African-American, Latino/a, Arab-American, Asian-American, European-American), wealth status (high/low), and immigrant-status (non-native student). These categories were selected based on the developmental science literature that has demonstrated that these target groups experience victimization and social exclusion in peer contexts during the elementary school years (Brown, 2017; Rutland & Killen, 2015). Other significant target groups that have experienced exclusion and discrimination, such as physical disability or gender non-conforming, were not included in the program due to the constraints of an 8-week curriculum program (with a limit of 8 target groups). However, by providing students with a variety of excluded groups it was expected that children would generalize the lessons learned to groups not covered explicitly by the program.

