An intervention to Promote Positive Peer Relationships and Reduce Prejudice and Bias in Childhood

Analysis Plan

16 July 2025

1. Hypotheses

- 1.1. We expected that compared to the control condition, participants in the treatment condition would:
 - 1.1.1. report higher **school belonging, peer support, and teacher support** at posttest.
 - 1.1.2. report lower levels of **personal experiences with exclusion** at posttest.
 - 1.1.3. report higher **contact with diverse peers** at posttest.
 - 1.1.4. report higher **desire to play with diverse peers** at posttest.
 - 1.1.5. more negatively **evaluate exclusion** at posttest.
 - 1.1.6. have higher **high-status occupation expectations** about marginalized groups (girls, Black peers, Latine peers) at posttest.
 - 1.1.7. make more positive **trait attributions** of diverse peers at posttest.
 - 1.1.8. have higher **expectations of inclusivity** of different peer groups at posttest.
 - 1.1.9. have more positive **math and science competency beliefs** about marginalized groups (girls, Black peers, Latine peers) at posttest.
- 1.2. We expected treatment effects to vary by participant race/ethnicity for school belonging, peer support, teacher support, personal experiences with exclusion, contact with peers of different race/ethnic groups, desire to play with peers of different race/ethnic groups, evaluations of exclusion of different race/ethnic groups, high status occupation expectations about marginalized racial groups, beliefs about the inclusivity of different race/ethnic groups, math and science competency beliefs about different race/ethnic groups, and trait attributions of different race/ethnic groups.
- 1.3. We expected treatment effects on the above listed outcome measures to vary by grade. Older children may exhibit greater change on these measures due to more awareness of group dynamics. However, a previous iteration of this program (conducted with a more racially homogeneous sample) found that compared to 5th graders, 3rd graders showed more change from pre to posttest.
- 1.4. Exploratory hypotheses: We tested for school effects due to differences in their racial composition. We also examined 2-way treatment interactions with school, race, and gender to determine whether the program was more effective for certain child demographic groups.

2. Measured variables

1. School belonging*
2. Peer support*
3. Teacher support*
4. Personal experiences with exclusion*
5. Reported contact
6. Desire to play

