7. Evaluations of exclusion
8. High status occupation expectations
9. Positive trait attributions*
10. Expectations of inclusivity
11. Math and science competency beliefs

**Indicates mean composite variable*

Measures also included in analyses, depending on model selection:

- Participant race/ethnicity (parent report)
- Gender (parent report)
- Grade level (3, 4, 5)
- Pretest measure for the respective outcome model was included as a control in each model
- School

Analysis Procedure

We first examined ICCs for classroom level and school level to determine if multilevel modeling was needed and conducted model comparisons to determine if classroom, school, and sex should be included as fixed effects. We selected models for each outcome variable based on lowest AIC and BIC.

We also conducted exploratory factor analyses on reported contact measures, desire to play measures, and evaluations of exclusion to determine if creating composite measures was most appropriate for analysis.

For all models, we included school, classroom, and gender if model comparisons indicate, using the model with lowest AIC and BIC for a given outcome variable.

We conducted multiple regression linear regression for all **composite variables**, using the base model:

```
lm(posttest DV ~ pretest DV + treatment*grade + race-ethnicity)
```

For all individual items for **reported contact, desire to play, evaluations of exclusion, expectations of inclusivity, and math/science competency beliefs**, we conducted ordinal logistic regression using the base model:

```
polr(posttest DV ~ pretest DV + treatment*grade + race-ethnicity)
```

For **high status occupation expectations**, we examined outcome distributions to determine if it is appropriate to collapse response options by stimuli gender and/or race. We conducted multinomial logistic regression using the base model:

```
multinom(posttest DV ~ pretest DV + treatment*grade + race-ethnicity)
```

Exploratory Analyses

For the above models, we tested the model removing the grade*treatment interaction, if it is not significant, to isolate the treatment effect. We also tested interactions of treatment*grade and treatment*gender to determine if the treatment was more effective for certain demographic groups.

Inference criteria

We considered predictors significant at a *p*-value of .05. We used Bonferroni adjustment for multiple groups pairwise comparisons.

Data exclusion

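### School, the block within which arms were assigned, is left to AIC/BIC selection outcome by outcome instead of being fixed in every model

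*SAP*

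**What the plan says.** The opening of the protocol states that "A multi-site within-school randomized control trial (RCT) intervention design was employed". Neither document gives the number of schools or classrooms, the allocation ratio by school, or whether the classroom or the child was the unit assigned.

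In the SAP, school appears in four places:

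- Measured variables: school is listed under the line "Measures also included in analyses, depending on model selection".
- Analysis Procedure: the base model for composites is "lm(posttest DV ~ pretest DV + treatment*grade + race-ethnicity", closed by a bracket. The polr and multinom base models have the same right-hand side. None contains school or classroom. The rule for adding them is that "we included school, classroom, and gender if model comparisons indicate", with AIC and BIC as the criteria, applied to each outcome separately. Before that, "We first examined ICCs for classroom level and school level to determine if multilevel modeling was needed"; no ICC value or threshold is given.
- Hypothesis 1.4, labelled exploratory: "We tested for school effects due to differences in their racial composition".
- Missing data: school is a predictor in the imputation model, which does not place it in the analysis model.

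No section keeps school in the models because it was the randomisation block. The SAP also does not say which criterion governs when AIC and BIC disagree.

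**The concern.** An analysis should respect the groups within which arms were assigned. Here the term that represents those groups may be present for one outcome and absent for the next, depending on how each fit turns out. Two things are at stake.

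First, with arms balanced inside every school, omitting school leaves between-school variance in the residual although the arm contrast is made within schools. The standard error is then too wide and some power is lost.

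Second, if the treated share varies from school to school, for example because a school has an odd number of classrooms, the unadjusted contrast partly compares schools with each other. The treatment estimate then carries school differences that the model's standard error does not reflect. The SAP itself expects schools to differ, and in racial composition, which is close to the subject of many of the outcomes.

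**Working it through.** The plan gives no power calculation, ICC or standard error, so there is no figure to reproduce.

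**Inputs from the documents.** N = 885 (Protocol, Settings and Participants); significance level 0.05 (SAP, Inference criteria), taken as two-sided; child-level lm (SAP, Analysis Procedure).

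**Assumptions.** School share of outcome variance, net of the model's covariates, 0.02 / 0.05 / 0.10; total variance 1; schools of equal size; 4 to 14 schools. Steps 1 to 3 also assume no classroom variance. The figures are for the linear model; polr and multinom were not calculated.

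**Step 1. Equal allocation within each school.** The true variance of the arm contrast is 4(1 − share)/885. A model without school reports about 4/885. The reported SE is therefore too wide by 1/sqrt(1 − share):

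- 0.02: 1/sqrt(0.98) = 1.010, type I error 4.8%
- 0.05: 1/sqrt(0.95) = 1.026, type I error 4.4%
- 0.10: 1/sqrt(0.90) = 1.054, type I error 3.9%

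Type I error here is 2·P(Z > 1.96 × ratio). Simulation (1,500 runs per setting; 4, 6 or 12 schools) agrees. With school always dropped, type I error was 0.036 to 0.059, and the SE was 5–6% too wide at share 0.10. Monte Carlo error near 0.05 is about ±0.011.

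**Step 2. Treated share differing between schools.** Let half of the S schools have treated share p and half 1 − p. With school omitted, the contrast gains variance 4(2p − 1)²·share/S.

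- *14 schools of 3 classrooms, 1 or 2 treated in each, share 0.05.* (2p − 1)² = 1/9, so the extra variance is 4 × (1/9) × 0.05/14 = 0.00159. Within-school variance is 4 × 0.95/885 = 0.00429. True SE = sqrt(0.00588) = 0.0767; reported SE is about sqrt(4/885) = 0.0672; ratio 0.88. Type I error = 2·P(Z > 1.96 × 0.88), about 9%. Simulation gave about 9% with school dropped or chosen by BIC, against about 5% with school included.
- *Stress case: 6 schools, 75:25 alternating with 25:75.* Simulated type I error:

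| School share | Always dropped | BIC-selected | AIC-selected | Always included |
|---|---|---|---|---|
| 0.02 | 0.141 | 0.121 | 0.062 | 0.047 |
| 0.05 | 0.253 | 0.123 | 0.055 | 0.053 |
| 0.10 | 0.373 | 0.082 | 0.053 | 0.051 |

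**Step 3. How often selection drops school.** With 6 schools, equal allocation and shares 0.02 / 0.05 / 0.10, BIC drops it in 87% / 44% / 15% of runs and AIC in 21% / 5% / 1%. The two criteria often disagree, and the SAP does not say which prevails.

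**Step 4. What including school does not do.** Suppose classrooms were assigned and classroom is left out of the model. With 18.4 children per class (885/48, assumed), the SE is too small by sqrt(1 + 17.4 × ICC) = 1.16 / 1.37 / 1.66 at classroom ICC 0.02 / 0.05 / 0.10. Type I error is 0.091 / 0.152 / 0.236. Simulation gave 0.08–0.10, 0.14–0.17 and 0.23–0.26, whether school was in or out.

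**The case against.** The strongest reply is that selection is a reasonable safeguard. AIC and BIC tend to discard school when it explains little and keep it when it explains much. With equal allocation, simulated type I error was 0.040 to 0.059 under either criterion, close to always including school. Under the stress allocation, AIC selection still gave 5–6%. School can also enter as a level after the ICC check. Every base model holds the pretest and race-ethnicity, so part of the school difference may already be removed. All of this stands, and it makes the consequence modest if arms were balanced within schools. It does not cover unequal allocation under BIC, and the documents do not show that allocation was equal.

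A reader might infer much larger losses from a calculation on classroom means. With 42 classrooms and classroom ICC 0.05, SE = sqrt(4v/42), and v gains the school share when school is omitted. The SE then widens by 10% / 24% / 45%, and power for a 0.25 SD effect falls from 77% to 44% at share 0.10. The arithmetic is right, but the SAP specifies no classroom-level analysis. In its child-level lm with balanced arms and no classroom variance, the same 0.25 SD effect at share 0.10 has power of 97.5% with school and 96.8% without.

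On cost, the SAP is written in the past tense, so the change means refitting models and not only rewording.

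**Conclusion.** The point holds as one of specification: the randomisation block is optional in all three model families and is decided by the data for each outcome. Its numerical effect cannot be settled from the documents, because allocation by school is not stated. Under balanced allocation it is small and conservative (SE about 1% to 5.4% too wide over the assumed shares). Under uneven allocation it is anti-conservative: about 9% type I error in the odd-classroom example and up to 12% under BIC selection in the stress case. These figures rest on assumed numbers of schools, shares and allocations.

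A reader might conclude that the standard errors are wrong in general, or that adding school would put them right. The documents support neither. With balanced arms the error from omitting school is slight. If classrooms were assigned, with classroom ICC 0.05 and 42 classrooms, type I error in the base lm is about 16–18% with or without school. The protocol describes delivery as "a group experience in which the teacher led a classroom discussion session that immediately followed students' use of the tool", so classroom clustering is a separate and probably larger threat.

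**What to change.** Include school as a fixed effect in every confirmatory model (lm, polr, multinom, or their mixed versions), giving as the reason that assignment was made within school. Remove school from the terms subject to model comparison. Report the number of classrooms and children per arm in each school, and state the unit of assignment. If models without school have already been fitted, present the school-adjusted results for all outcomes.

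The cost is a rerun on the 30 imputed datasets and a few degrees of freedom out of 885 children. It is somewhat heavier in multinom, where each school indicator adds a parameter for every non-reference category.

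Classroom clustering needs its own provision if classrooms were the assigned unit, for example a random classroom intercept. Classroom fixed effects would not serve, since they would be collinear with treatment.

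### Hypothesis 1.1 is an overall treatment effect, but the SAP isolates that effect only when the treatment-by-grade interaction is not significant and defines no test of it otherwise

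*SAP*

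**What the plan says.** SAP section 1.1 introduces its list of outcomes with "We expected that compared to the control condition, participants in the treatment condition would". No grade is named, so this is an overall comparison at posttest. Section 1.3 adds "We expected treatment effects on the above listed outcome measures to vary by grade" and leaves the direction open. It says "Older children may exhibit greater change on these measures due to more awareness of group dynamics", then reports that an earlier run of the programme saw more change in grade 3 than in grade 5.

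Under Analysis Procedure, the base model for composite outcomes is "lm(posttest DV ~ pretest DV + treatment*grade + race-ethnicity". The ordinal (polr) and multinomial (multinom) base models have the same right-hand side. Grade is listed with levels 3, 4 and 5, but the SAP does not say whether it enters as a factor, with which reference level, or with which contrasts.

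The only step described as isolating the treatment effect is under Exploratory Analyses: "we tested the model removing the grade*treatment interaction, if it is not significant, to isolate the treatment effect". Inference criteria sets the 0.05 level and applies Bonferroni to pairwise comparisons of groups, without naming a grade contrast. Missing data says that analyses were run on 30 imputed datasets and pooled results reported.

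**The concern.** Once a model contains treatment*grade, no single coefficient is the treatment effect until the coding or a contrast is fixed. If grade is a factor under R's default coding, the coefficient labelled treatment is the effect in grade 3 alone. Under sum-to-zero coding it is the equal-weight average over the three grades. The SAP gives neither a coding nor an averaged contrast.

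The stated rule then gives Hypothesis 1.1 two possible answers. If the interaction is not significant, the answer comes from the main-effects model. If it is significant, the SAP does not say what the answer is. With 11 measured variables, some may fall in one branch and some in the other, so results presented as tests of one hypothesis may concern different quantities. The undefined branch is the one to expect if section 1.3 is right.

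**Working it through.** The documents give no effect size, SD or power figure, so there is nothing of the plan's to reproduce. The numbers below only illustrate the consequence of the rule.

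**Inputs.** From the documents: N = 885 (Protocol, Settings and Participants), three grades, level 0.05. Assumed: two-sided tests, equal grades (885/3 = 295 pupils each), 1:1 allocation, residual SD 1, no clustering, linear model. Assumed grade effects have mean 0.20 SD, except under the null.

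**Standard errors**
- Effect in one grade: sqrt(4/295) = 0.1164.
- Grade-averaged effect: 0.1164/sqrt(3) = 0.0672.

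**Averaged contrast, always reported.** Power at 0.20 is Phi(0.20/0.0672 − 1.96) = 84%, whatever the grade pattern. Type I error is 5.0%.

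**The SAP's rule, completed in two ways.** First do a joint 2-df interaction test at 0.05. If it is not significant, test the main-effects treatment term. If it is significant, either (A) read the grade 3 coefficient, or (B) test each grade with Bonferroni and look for at least one positive grade.

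The average and the interaction test are independent here, so reading A can be checked by hand from the simulated conditional rates:
- Null: 0.95 × 0.05 + 0.05 × 0.311 = 0.0475 + 0.0156 = 6.3%.
- Effects 0/0.2/0.4 (interaction significant in 57.7%): 0.423 × 0.845 + 0.577 × 0.048 = 0.357 + 0.028 = 39%.
- Effects 0.4/0.2/0 (interaction significant in 57.6%): 0.424 × 0.845 + 0.576 × 0.982 = 0.358 + 0.566 = 92%.

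Simulated rejection rates:

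| Effects in grades 3/4/5 | Averaged contrast | A: grade 3 coefficient | B: within-grade tests |
|---|---|---|---|
| 0/0/0 | 5.0% | 6.3% | 7.1% |
| 0.2/0.2/0.2 | 84% | 83% | 85% |
| 0.1/0.2/0.3 | 84% | 71% | 87% |
| 0.3/0.2/0.1 | 84% | 86% | 87% |
| 0/0.2/0.4 | 84% | 39% | 92% |
| 0.4/0.2/0 | 84% | 92% | 92% |

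**Range.** If the pretest explains half the variance (R² 0.5), reading A gives 15.6% against 99.8% for the two steep patterns, and the averaged contrast 99%. Clustering lowers power: with a design effect of 2.0 the averaged contrast falls to 56%, and for the steep pattern reading B gives 66%.

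**The case against.** Keeping an interaction when the data support it, dropping it otherwise, and interpreting effects by grade when it is kept is common practice. Section 1.3 makes grade variation a planned finding. If effects differ by grade, an average depends on its weights and may describe no grade well. Within-grade follow-up loses no detection: column B is at or above the averaged contrast in every pattern, and the added type I error is small. With a uniform effect, little changes under either reading. All of this stands. It does not fill the gap, because an effect in at least one grade is not the overall effect in section 1.1, and the SAP does not say that within-grade tests are its Hypothesis 1.1 result.

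Three stronger readings are tempting and are not supported.
- A reader might infer a large loss of power, because the main-effects model is both fitted and significant in only 36% of trials with a 0 to 0.4 spread, against 84% for the average. That count treats every significant interaction as a failure to detect, although the plan treats it as a finding.
- A reader might infer that grade was entered as a number, so that the treatment coefficient is an extrapolation to grade 0. Nothing in the documents says so. The contrast of 3rd with 5th graders and the reference to pairwise group comparisons fit grade as groups, though neither fixes the coding.
- A reader might infer that the interaction decision was made separately in each imputed dataset. The Missing data section says pooled results were reported, and a pooled decision is the natural reading. This is at most a clarification.

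**Conclusion.** The concern holds as an omission with a consequence: the SAP's own rule lets a preliminary p-value decide, outcome by outcome, which quantity answers Hypothesis 1.1, and leaves that hypothesis without a defined test after a significant interaction. This rests on the text alone and applies to the linear, ordinal and multinomial models alike.

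The size depends on assumptions outside the documents and was worked out only for the linear model. The type I cost is modest, about 1 to 2 percentage points per outcome. The effect on detection runs from negligible (uniform effects) to large and dependent on direction (grade 3 reading, steep gradient). Section 1.3 names both directions, so the favourable one cannot be assumed. The point should be fixed. It does not show that any reported result is wrong, since the documents do not say which completion of the rule was used.

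**What to change.** - Delete the condition that the interaction be non-significant, and state that grade is a factor.
- For every outcome, test Hypothesis 1.1 with one grade-averaged treatment contrast from the interaction model, on that model's own scale, whatever the interaction p-value. State the weights, for example the sample's grade proportions. Compute the contrast in each of the 30 imputed datasets and pool.
- Test Hypothesis 1.3 separately with the joint treatment-by-grade test, and report the grade-specific effects beside the average.
- The SAP is written in the past tense, so label the averaged contrast post hoc unless it was documented before the analysis.

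The cost is revised wording and one extra contrast per outcome, with no new data. The drawback is that the average must be read with the grade-specific effects when grades differ.

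### SAP hypothesis 1.2 expects treatment effects to differ by race/ethnicity, but no written model contains a treatment-by-race term, and its status beside 1.4 is unclear

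*SAP*

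**What the plan says.** **Hypotheses.** SAP 1.2 carries no exploratory label. It begins "We expected treatment effects to vary by participant race/ethnicity for school belonging, peer support, teacher support" and continues through every measured construct. Four constructs are unrestricted (belonging, peer support, teacher support, experiences of exclusion). The other seven appear in race-related versions, for example "high status occupation expectations about marginalized racial groups, beliefs about the inclusivity of different race/ethnic groups". SAP 1.4, headed as exploratory, names the interaction again without listing outcomes: "We also examined 2-way treatment interactions with school, race, and gender".

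**Models.** Under Analysis Procedure the composites are analysed with "lm(posttest DV ~ pretest DV + treatment*grade + race-ethnicity". The `polr` model, for individual items on "reported contact, desire to play, evaluations of exclusion, expectations of inclusivity, and math/science competency beliefs", and the `multinom` model, for occupation expectations, have the same right-hand side.

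**Model selection.** The list headed "Measures also included in analyses, depending on model selection" contains variables, not interactions. The selection step itself is described as "conducted model comparisons to determine if classroom, school, and sex should be included as fixed effects".

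**Exploratory Analyses.** After a step that drops a non-significant grade interaction, the section says "We also tested interactions of treatment*grade and treatment*gender to determine if the treatment was more effective for certain demographic groups".

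**Protocol.** Aim 1 concerns ethnic differences at baseline. Aims 2 and 3 state only the overall comparison with control.

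**The concern.** A hypothesis that an effect differs between groups needs a term that lets it differ. Hypothesis 1.3, on grade, has its interaction in every base model; 1.2, stated in the same form, has none. The one sentence that could have supplied it names grade a second time and omits race and school, two of the three interactions in 1.4.

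Two things are at stake. An analyst who follows the written models produces no test of 1.2. And if a race-specific result is reported, a reader cannot determine from the documents whether it tests the expectation in 1.2 or is an exploratory finding under 1.4. This matters in a program aimed at intergroup bias in an ethnically diverse district, and all the more because the SAP is written in the past tense.

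**Working it through.** The documents give no power calculation or sample-size figure for this test, so there is nothing to reproduce. The check is of model terms; the arithmetic that follows is only an illustration of precision.

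**1. Terms in each written model.** I took three grades, the five race/ethnicity groups listed in the protocol (the SAP does not give the coding) and one pretest column.

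| Model | Columns | Interaction columns |
|---|---|---|
| Base model | 11 | treatment-by-grade: 2 |
| Base plus gender main effect | 12 | treatment-by-grade: 2 |
| Base plus treatment-by-gender | 13 | treatment-by-grade: 2; treatment-by-gender: 1 |
| Base plus treatment-by-race (not written in the SAP) | 15 | treatment-by-grade: 2; treatment-by-race: 4 |

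The base count is 1 intercept + 1 pretest + 1 treatment + 2 grade + 4 race + 2 interaction = 11. No written model has a treatment-by-race column. Adding school or classroom as a fixed effect does not create one. Within a grade, each model therefore imposes one treatment effect, on its link scale, for all race groups.

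**2. Scope.** Five starred composites by `lm`, five constructs by `polr` and one by `multinom` make 5 + 5 + 1 = 11 constructs. Factor analysis that might yield composites is planned for only three of the five `polr` constructs (contact, desire to play, evaluations of exclusion). The number of items is not given, so the number of models cannot be fixed from the documents.

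**3. Degrees of freedom of the missing test.** With five groups, 5 − 1 = 4 for `lm` and `polr`. For `multinom`, 4 multiplied by (response categories − 1).

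**4. Precision for a composite.** From the protocol: N = 885. Assumed: outcome SD 1, 1:1 allocation, five equal groups (885 / 5 = 177), pretest-posttest correlation r of 0.5 to 0.7, no clustering, two-sided .05, and a true effect of 0.30 SD in two groups and 0 in three.

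- Average effect, which is what a model without the interaction reflects: (2/5) × 0.30 = 0.12 SD.
- Sum of squared deviations from that average: 2 × 0.18² + 3 × 0.12² = 0.108.
- Noncentrality: 0.108 × (177/4) / (1 − r²), which is 4.779/0.75 = 6.37 at r = 0.5 and 4.779/0.51 = 9.37 at r = 0.7.
- Power of the 4-df test (noncentral chi-square): 0.497 and 0.684.
- 95% half-width of one group's effect: 1.96 × 2 × √(1 − r²) / √177 = 0.255 SD at r = 0.5 and 0.210 SD at r = 0.7.

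**The case against.** The strongest reply is that 1.4 says treatment-by-race was examined. The formulas are called base models, Exploratory Analyses adds terms to them, and its purpose clause closely follows that of 1.4. The natural reading is then that the race term was added to the base model. This stands to a point: a reader might infer that race moderation was never looked at, and the documents do not support that. What is missing is the formula, the joint test, the outcomes and the status.

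A reader might also infer that the repeated grade interaction is a slip for race. It may be, but nothing confirms it. If it is, the test sits under Exploratory Analyses and the tension with 1.2 remains.

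It can be argued that 1.2 and 1.4 divide the work, with 1.4 covering versions that 1.2 leaves out, such as stimuli about girls. The SAP does not say so, but this makes the two sections ambiguous rather than flatly contradictory.

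Finally, the power illustration rests almost wholly on assumed inputs and has no bearing on whether the term is missing. That is correct. Nor should it be marked down by a standard design effect. Under classroom assignment with racially balanced classes and random intercepts only, a check with an assumed 40 classes of 20 and intraclass correlation 0.05 gave an interaction variance of 0.0475, against 0.0500 without clustering. Loss of precision would need racially uneven classes or race-specific class effects, which the documents do not describe.

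**Conclusion.** The point holds as a specification gap and should be fixed. Followed as written, the Analysis Procedure and Exploratory Analyses cannot test 1.2 for any of the 11 constructs. Exploratory Analyses also does not match 1.4, and race moderation is an unlabelled expectation in one place and exploratory in another. This rests on the text alone.

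A reader might go further and doubt the main results. The documents do not support that: the average effects in 1.1 do not depend on this term. Error control across outcomes is a separate question and not part of this point.

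On the assumptions in the working, the joint test on a composite has about 50 to 68% power, and a group of 177 has its effect estimated to within about 0.21 to 0.26 SD. Even with the term added, a non-significant joint test would be weak evidence that effects are alike across groups.

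**What to change.** 1. For each outcome or item under 1.2, fit the selected model plus treatment by race/ethnicity. State the race coding, and whether the grade interaction is retained when the SAP's removal step applies. Use one joint treatment-by-race test per model, pooled over the 30 imputations (for example a pooled multivariate Wald test), and report race-specific effects with intervals.
2. Give race moderation one status in 1.2, 1.4 and the analysis sections, and disclose when the test was specified. Label it exploratory unless that was before results were seen.
3. Correct the Exploratory Analyses sentence to agree with 1.4: say whether the repeated grade interaction was meant as race, and include treatment by school. If race moderation is declared confirmatory, place it in the main analysis section instead.

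As a secondary check, confirm that the imputation model allows a treatment-by-race interaction. The Missing data section mentions none, but that does not show that none was used.

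The cost is SAP wording, a disclosure of timing, and one extra model per outcome or item. Race/ethnicity is already collected by parent report. The drawback is the limited precision shown above, which should be stated beside the results.
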